### **5.1.7 Neurological Examination**

Neurological examination results collected through the study include:

1. Visual impairment assessment performed and result, if performed,
2. Mental status assessment performed and result, if performed,
3. Cranial nerves function assessment performed and result, if performed,
4. Motor function assessment performed and result, if performed,
5. Sensory function assessment performed and result, if performed,
6. Cerebellar function assessment performed and result, if performed.

For each assessment performed, the result is assessed as Normal / Abnormal.

Neurological examination results will be presented by visit in a frequency table.

Neurological examination data will be listed.

## **5.2 Secondary Endpoints**

All efficacy summaries described below will be analyzed using the Efficacy Population; listings will use All Screened Subjects.

### **5.2.1 Unified Batten Disease Rating Scale (UBDRS)**

The UBDRS assessment consists of several domains with individual questions within each domain. The assessments will be collected at the visits as shown in the protocol schedule of events. UBDRS domains measured, corresponding questions and relevant imputation rules are described in [Table 2](#) below. Subscales of Physical Assessment domain are also derived and described in [Table 2](#).

**Table 2. UBDRS Domains/Subscales and Analysis Methods**

Domain	Contributing Questions	Method of Summarization	Imputation Rules
Physical Assessment	1, 1A, 2, 3, 4A, 4B, 5A, 5B, 6, 7A, 7B, 8A, 8B, 9A, 9B, 10A, 10B, 11, 12, 13, 14A, 14B, 15, 16, 17, 18, 19, 20	Sum of scores of individual questions divided by number of questions (28).	Missing or not done individual question values will be imputed with the worst possible value (i.e., 4) for summaries
Modified Physical Assessment Subscale	1, 1A, 3, 4A, 4B, 5A, 5B, 6, 9A, 9B, 11, 12, 13, 14A, 14B, 19	Sum of scores of individual questions divided by number of questions (16).	As for Physical Assessment domain
Physical Assessment 5-item Subscale	1, 11, 12, 13, 19	Sum of scores of individual questions divided by number of questions (5).	As for Physical Assessment domain
Physical Assessment 2-item Subscale	1, 12	Sum of scores of individual questions divided by number of questions (2).	As for Physical Assessment domain
Seizure Assessment	23-34	Sum of scores of individual questions divided by number of questions (12).	Missing or not done individual question values will be imputed with the worst possible value for summaries: 1. Questions 23, 25, 26, 27, 29 – 6, 2. Questions 24, 28, 30 – 5, 3. Questions 31, 32 – 3. 4. Question 33 – 2, 5. Question 34 – 1.
Behavioral Assessment (Past Month)	36A, 36B, 37A, 37B, 38A, 38B, 39A, 39B, 40A, 40B, 41A, 41B, 42A, 42B, 43A, 43B, 44A, 44B, 45	Sum of scores of individual questions divided by number of questions (19).	Missing or not done individual question values will be imputed with the worst possible value for summaries: 1. Question 45 – 1, 2. All other questions – 3.
Capability Assessment Given Actual Vision	52-56	Sum of scores of individual questions divided by number of questions (5).	Missing or not done individual question values will be imputed with the worst possible value for summaries: 1. Questions 52-55 – 3, 2. Question 53 – 2.
Clinical Summary	61-67	Each question (including 6 CGIs*** and one assessment of change) will be presented separately.	Missing or not done individual question values will be imputed with the worst possible value for summaries (5).  Question 61 (Assessor's global impression of change since last assessment) value "Not applicable (never seen before)" will not be imputed.

\* NCL history domain of UBDRS (completed by first rater) will be summarized with baseline disease history data

(see details in section [5.7](#)).

\*\* Capability assessment assuming normal vision is not assessed in this study.

\*\*\* CGI = Clinician Global Impression.

Domain scores, subscale scores and individual question scores (only for Clinical Summary domain which does not have domain score), and their respective changes from baseline will be summarized at each scheduled post-baseline visit. Baseline will be defined as last value collected before first study drug administration; both data collected at scheduled and unscheduled visits will be included in baseline derivation. For Clinical Summary domain question 61 (Assessor's global impression of change since last assessment), only observed values (not change from baseline) are presented.

UBDRS data (including both individual and domain scores) will be listed.

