#### 7.3.1 Unified Batten Disease Rating Scale

The UBDRS is a scale specifically developed to assess symptoms in CLN3 subjects ([Marshall 2005 et al., Kwon et al., 2011, Cialone et al., 2012., Masten et al., 2020](#)). The UBDRS consists of 7 different domains: (1) physical, (2) seizure, (3) behavioral, (4) capability normal vision (will not be assessed) (5) capability actual vision, (6) NCL history and (7) clinical summary including 7 global impression scales (Appendix 2). The physical domain consists of 20 different items based on a neurological assessment; higher scores indicate more severe disease. The seizure domain consists of 12 different assessments based on parent/caregiver information: frequency of seizure types (8 items), medical consequences of seizures (4 items), higher scores indicate more severe disease. The behavior domain consists of 10 different assessments based on parent/caregiver information; higher scores indicate more severe disease. The capability domain has 5 different assessments based on parent/caregiver information; lower scores indicate more severe disease, and NCL history including 8 items to document the onset of typical symptoms. The UBDRS assessments via live video -interview will be performed at the time points outlined on the Schedules of Assessments, if video interview is not possible for technical reasons, patients will be assessed at the NIH by a UBDRS trained rater. In cases of any event precluding safe travel by participants to NIH, the assessment will be performed remotely according to instructions delivered by Rochester University ([Section 1.3](#)). A copy of the UBDRS is provided in [Section 13.2](#) . In case of sedation for other examinations (e.g. MRI, OCT, lumbar puncture), UBDRS will be performed either before or  $> 24$  hours after sedation.

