### NEURONAL CEROID LIPOFUSCINOSIS (NCL) STUDY GROUP UNIFIED BATTEN DISEASE RATING SCALE

All items must be completed. Use U if information is Unavailable or Not Applicable.

SUBJECT NO.    INITIALS (First, Middle, Last)    SITE NO.

DATE INFO OBTAINED (mm/dd/yyyy)

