52. SCHOOL

52.

0 = normal ability in mainstream classroom  
1 = marginal ability in mainstream classroom  
2 = requires special needs classroom  
3 = unable to attend special needs classroom

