56. CARE LEVEL

56.

0 = home  
1 = chronic care at home  
2 = full time skilled nursing

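### Worst-value imputation of missing UBDRS items feeds into change from baseline, where a gap at one visit only can look like worsening or improvement; the Capability row of the rule also contradicts itself

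*SAP*

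**What the plan says.** SAP 5.2.1, Table 2, defines each domain or subscale score as the item sum over a fixed number of items: 28 (Physical), 16, 5 and 2 (its subscales), 12 (Seizure), 19 (Behavioral) and 5 (Capability). For Physical, "Missing or not done individual question values will be imputed with the worst possible value (i.e., 4) for summaries"; the subscales follow it. The Seizure, Behavioral and Capability rows each list their own worst values. The Clinical Summary items (61–67) are presented singly, and a missing one becomes 5.

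The text after the table says of the domain, subscale and Clinical Summary scores that "their respective changes from baseline will be summarized at each scheduled post-baseline visit". Item 61, the assessor's impression of change, is the exception: its not-applicable category is not imputed, and "only observed values (not change from baseline) are presented".

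The Capability row, which covers items 52–56, reads "Questions 52-55 – 3, 2. Question 53 – 2" (the 2 before the second Question is a list number). On the form in Protocol Appendix 2, item 53 runs to 3 and item 56 ends at "2 = full time skilled nursing". Protocol 7.3.1 says "The capability domain has 5 different assessments based on parent/caregiver information; lower scores indicate more severe disease", yet the form scores item 52 upwards from 0 for normal ability to "3 = unable to attend special needs classroom", and the SAP imputes 3 as worst.

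The form also instructs raters: "All items must be completed. Use U if information is Unavailable or Not Applicable".

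**The concern.** Scoring an unrated item at its worst is cautious for a single score. It is not cautious for a difference between two scores. If the item is rated at one visit and missing at the other, the difference mixes a real rating with an assigned one. A follow-up gap can then look like progression and a baseline gap like benefit.

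The schedule of activities places the UBDRS only once before dosing, at Visit 2, so a baseline gap will normally have no earlier value to replace it. SAP 5.12 provides a row for non-missing observations, but once values are imputed that row need not show how many items were rated. With six subjects, one gap in a short subscale or a single global impression is visible in the mean, and the table would not say why.

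The Capability row is a separate matter. Applied literally, it mis-scores one item and leaves another without a listed value.

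**Working it through.** **Inputs.** Divisors and imputed values come from SAP Table 2, item maxima from Protocol Appendix 2, and six subjects from SAP 2.2. The missing-item rate is not stated, so all figures below are per item missing at one visit only. The true values v are assumed ranges.

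**The plan's own figures.** Counting the listed questions reproduces every divisor: 28, 16, 5, 2, 12, 19 and 5. The listed worst values match the form in every row except Capability.

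**False change from one gap.** With the true value unchanged at v, the shift is (worst − v)/k. It is positive (worsening) if the item is missing at follow-up, negative (improvement) if missing at baseline, and zero if v is already worst.

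| Score | k | Worst | v | Shift, one subject | Shift, mean of six |
|---|---|---|---|---|---|
| Physical | 28 | 4 | 1 to 3 | 3/28 = 0.107 to 1/28 = 0.036 | 0.018 to 0.006 |
| Modified Physical | 16 | 4 | 1 to 3 | 3/16 = 0.188 to 1/16 = 0.063 | 0.031 to 0.010 |
| 5-item | 5 | 4 | 1 to 3 | 3/5 = 0.60 to 1/5 = 0.20 | 0.100 to 0.033 |
| 2-item | 2 | 4 | 1 to 3 | 3/2 = 1.5 to 1/2 = 0.5 | 0.250 to 0.083 |
| One global impression (62–67) | 1 | 5 | 2 to 4 | 3 to 1 | 0.50 to 0.167 |
| Seizure, one frequency item | 12 | 6 | 0 to 5 | 6/12 = 0.50 to 1/12 = 0.083 | 0.083 to 0.014 |
| Behavioral, one item scored 0–3 | 19 | 3 | 0 to 2 | 3/19 = 0.158 to 1/19 = 0.053 | 0.026 to 0.009 |

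**A baseline gap hiding decline.** Suppose every item truly goes from 2 to 3 and one is missing at baseline.
- 2-item: 3.0 − (2 + 4)/2 = 0, against a true +1.
- 5-item: 3.0 − (4×2 + 4)/5 = 3.0 − 2.4 = +0.60, against a true +1.

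**What a table of items answered at both visits adds.** Assume 10 of 28 Physical items are unanswered at one visit and true baseline values are 2, so the imputed shift is 10×(4 − 2)/28 = 0.714.
- Gap at follow-up, no true change: SAP +0.714, both-visit items 0, truth 0.
- Gap at follow-up, those ten truly worsen to 4: SAP +0.714, both-visit items 0, truth +0.714.
- Gap at baseline, no true change: SAP −0.714, both-visit items 0, truth 0.

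Neither table is right in every case, but the pair shows how far the result depends on the gap.

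**Why agreement between the two tables cannot be the test for interpretation.** Suppose one item is missing at both visits and the other 27 truly rise by 1. The SAP gives 27/28 = 0.96 and the both-visit table 1.0. With ten missing at both visits the figures are 18/28 = 0.64 and 1.0. The tables differ although no one-visit gap exists.

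**Capability.** A blank item 53 scored 2 instead of the form maximum 3 is off by (3 − 2)/5 = 0.20. If a blank item 56 added nothing instead of 2, the error would be 2/5 = 0.40, but that requires ignoring the worst-value instruction that opens the same cell.

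**Items 24, 28 and 30.** The form scores none or not applicable as 0. If such a case were instead entered as U and imputed as 5, each item would add 5/12 = 0.42, and all three 15/12 = 1.25. Whether this can happen depends on the eCRF, which is not available here.

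**The case against.** The strongest defence is that an unrated item in a degenerative disease often means lost ability, and the form itself gives 4 to inability on several items (cannot walk, cannot stand). A worst value for items not done fits that scale. This stands as a reason to keep the worst-value table. It does not cover a baseline gap, nor an item unrated for other reasons; inability already has its own score, and the form keeps a separate code for unavailable information.

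The endpoint is a descriptive secondary one, no test depends on it, and individual and domain scores are listed, so gaps in six subjects can be traced. That stands and limits the weight of the point. The largest Physical shift also needs speech or gait to be unrated, items that a trained rater sees directly.

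Three stronger readings are tempting but not supported:
- *The Capability rule cannot be programmed.* The general instruction and the form maxima make it evident that the second entry was meant for item 56.
- *Every U entry is scored as worst, so U should be dropped from the score.* Table 2 does not say how U is treated, and the eCRF may settle it. U also covers unavailable information, so dropping all U codes would remove most of the imputation that the worst-value table exists to make.
- *A blank item 61 will appear as the worst category of change.* Table 2 exempts only the not-applicable answer, but the later words "only observed values (not change from baseline) are presented" may or may not cancel imputation. The text is ambiguous.

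**Conclusion.** The rule is not conservative for change from baseline. One item missing at one visit only, with an unchanged true value below worst, produces a false change in either direction. The effect is small on the 28-item score and material on the 5-item and 2-item subscales and on single global impressions. The sizes assume the stated true values. How often gaps will occur is not given.

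A reader might infer that the UBDRS results will be biased in a known direction. The documents do not support this: live video is the planned mode throughout, all domains are to be administered at baseline, and nothing shows whether baseline or follow-up gaps are likelier.

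The Capability row is wrong as written: item 53 has two values and item 56 none. It is an evident slip, worth 0.20 on a blank item 53 if followed literally. The score direction in Protocol 7.3.1 conflicts with both the form and the SAP. These points should be fixed before the SAP is final, but they affect no test or decision rule.

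**What to change.** 1. Correct the Capability row to 3 for items 52–55 and 2 for item 56, and reconcile the Capability direction in Protocol 7.3.1 with the form and SAP.
2. Keep the worst-value table. Beside it, show change over items answered at both baseline and that visit, with the number of imputed items per subject and visit. Present this as a sensitivity display and flag subject-visits with items imputed at one of the two visits only. Do not make agreement of the two tables a condition for interpretation. The SAP already footnotes imputed adverse-event assessments (5.1.1), so disclosure of this kind is in keeping with it.
3. Show blank items 62–67 as missing, with n, instead of 5, and state that a blank item 61 is likewise not shown as the worst category.
4. Check against the eCRF that not-applicable entries for items 24, 28 and 30 are scored 0, as the form provides. Do not exclude all U codes from the score.

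The cost is SAP wording and one extra table before database lock, with no new data. The both-visit table may understate decline if items were not done because ability was lost, which is why the worst-value table stays. Neither table recovers change in items missing at both visits.

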**All items must be completed. Use U if information is Unavailable or Not Applicable.**

**IV. CAPABILITY ASSESSMENT ASSUMING  
NORMAL VISION (answer as if child's  
vision were normal)**

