53. CHORES

53.

0 = able to do all age appropriate chores  
independently  
1 = able to do simple chores independently  
2 = able to do simple chores with help  
3 = unable to do even simple chores

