## **2.2 Study Sample Size Determination**

A total of six subjects will be enrolled in the study. Due to the ultra-rare nature of CLN3 disease, sample size is based on subject availability and not a statistical determination.

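### SAP Table 2 gives UBDRS Capability item 53 two imputed values and item 56 none, and protocol 7.3.1 states the scale's direction in reverse

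*SAP*

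**What the plan says.** SAP 5.2.1, Table 2, defines the Capability domain (given actual vision) as items 52 to 56, added and divided by 5. For missing items the row first gives a general rule: "Missing or not done individual question values will be imputed with the worst possible value for summaries". It then itemises the values: "Questions 52-55 – 3, 2. Question 53 – 2". The isolated 2 before the full stop numbers the second entry, so the list has two entries: 3 for items 52 to 55, and 2 for item 53.

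The form in protocol Appendix 2 sets the range of each item. The top code is "3 = unable to attend special needs classroom" for School (item 52) and "3 = unable to do even simple chores" for Chores (item 53). Play (54) and ADL (55) also end at 3. Care level (56) ends at "2 = full time skilled nursing". In every case 0 is the best state.

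On direction, protocol 7.3.1 says that low scores in the capability domain go with worse disease. SAP 1.1 lists two departures from the protocol, one on the MedDRA levels used in adverse event tables and one on dictionary versions. Neither concerns the UBDRS.

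**The concern.** The itemised list is what a programmer would code from, and it contradicts the general rule in the same table cell. Item 53 lies inside the range 52 to 55, so it carries two values, and only one of them is its worst code. Item 56 belongs to the domain but has no listed value.

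The affected output is the domain score of a secondary efficacy scale. SAP 5.2.1 says of the domain scores that "their respective changes from baseline will be summarized at each scheduled post-baseline visit", so a wrong imputed value enters both the score at that visit and the change from baseline. Missing items are foreseeable: the form instructs raters "Use U if information is Unavailable or Not Applicable", and the SAP saw the need for a rule.

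The direction statement is a second problem in the same domain. Someone reading the results with protocol 7.3.1 in hand would take a rising Capability score as improvement, when on the form it means loss of function. The protocol sentence also cannot be used to settle the imputation question, because read literally it would make 0 the worst value for every item.

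**Working it through.** **Inputs.** Domain items, divisor and imputed values: SAP 5.2.1, Table 2. Item ranges: protocol Appendix 2, section V of the form. Number of subjects: SAP 2.2 ("A total of six subjects will be enrolled in the study").

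**1. The plan's own divisors.** Items 52 to 56 number 56 − 52 + 1 = 5, which agrees with the stated divisor. Counting the question lists for the other domains also reproduces Table 2: Physical 28, Modified Physical 16, Seizure 12, Behavioral 19.

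**2. Coverage of the itemised lists.**

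| Domain | Items given a value | Items in domain |
|---|---|---|
| Seizure | 5 + 3 + 2 + 1 + 1 = 12 | 12 |
| Behavioral | 1 + 18 = 19 | 19 |
| Capability | 52, 53, 54, 55 = 4 (53 twice) | 5 |

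The Seizure and Behavioral lists cover each item exactly once. Capability is the only itemised list that does not.

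**3. Listed value against the form.**

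| Item | Worst code on form | Value(s) in Table 2 |
|---|---|---|
| 52 School | 3 | 3 |
| 53 Chores | 3 | 3 and 2 |
| 54 Play | 3 | 3 |
| 55 ADL | 3 | 3 |
| 56 Care level | 2 | none |

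Reading the second entry as item 56 gives each item one value, equal to its worst code.

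**4. Scale range.** Domain score = sum of items / 5, so the maximum is (3 + 3 + 3 + 3 + 2) / 5 = 14 / 5 = 2.8.

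**5. Effect on one subject at one visit.**
- Item 53 missing and scored 2 instead of 3: (3 − 2) / 5 = 0.2 too low; 0.2 / 2.8 = 7% of the range. A one-step change on a single item is also 1 / 5 = 0.2.
- Item 56 missing and left out of the sum, divisor kept at 5: (2 − 0) / 5 = 0.4 too low; 0.4 / 2.8 = 14% of the range.
- All five items missing: 14 / 5 = 2.8 with item 53 as 3 and item 56 as 2; 13 / 5 = 2.6 with both as 2; 12 / 5 = 2.4 with item 53 as 3 and item 56 left out; 11 / 5 = 2.2 with item 53 as 2 and item 56 left out.

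**6. Effect on the group mean, six subjects, one affected.** Item 53: 0.2 / 6 = 0.03. Item 56: 0.4 / 6 = 0.07.

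**7. Sign of the error in change from baseline.** Higher means worse. If the low value falls at a post-baseline visit, worsening is understated. If it falls at baseline, worsening is overstated. If the same item is missing and handled in the same way at both visits, the error cancels.

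**8. Direction.** The form has 0 as best and 3 (or 2) as worst. Table 2 imputes the high codes as worst, in agreement with the form. Protocol 7.3.1 says the reverse. Taken literally, it would give an all-missing score of 0 instead of 2.8.

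**The case against.** The strongest reply is that this is a one-digit misprint which the document itself resolves. The general rule asks for the worst value, the form supplies it for all five items, and only one correction makes the list coherent. A programmer who checks the form will reach the right answer, and the 0.4 case arises only if the general rule is overlooked. That reading is very probably correct. It does not make the written instruction harmless: following the second entry as printed gives a wrong score for item 53, and following the right reading means departing from the SAP.

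The reply on size also has weight. The effect needs item 53 or 56 to be missing. The form asks raters to complete every item, the capability items come from the caregiver, and the UBDRS can be done remotely. The documents do not say whether a U entry counts as missing. Efficacy is descriptive, no test or decision rests on this score, and the listings show individual items. All of this limits the point to a correction and gives no reason to doubt the analysis as a whole.

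On direction, it can be said that the protocol sentence is descriptive, that it sits beside a reference to the form, and that SAP 1.1 is meant for changes to analyses. The last point is fair, and correcting the protocol sentence is the cleaner route. But SAP 5.2.1 never states a direction for this score in words, so the only explicit statement in either document is the wrong one.

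**Conclusion.** The point holds on both counts. Table 2 assigns item 53 two values, only one of which is its worst code, and assigns item 56 none. Protocol 7.3.1 states a direction opposite to the form and to the SAP.

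The numerical effect is conditional and small. It applies per subject and visit, only when item 53 or 56 is missing, and is 0.2 or 0.4 on the 0 to 2.8 scale. These figures assume that U is handled as missing. The item 53 figure also assumes that the second entry is applied. The item 56 figure assumes that only the itemised list is programmed and that the divisor stays at 5. When both items are observed, the imputation error has no effect.

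The direction error changes no computed number. It bears on the reading of every Capability change score, whether or not data are missing. The correction should be made, but nothing here undermines the study's primary safety objective.

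**What to change.** 1. In SAP Table 2, Capability row, change the question number in the second entry from 53 to 56. All five imputed values then match the form.
2. In protocol 7.3.1, reverse the stated direction for the capability domain so that it agrees with Appendix 2. If the protocol is not to be amended for this, record the difference in SAP 1.1.
3. Add one sentence to SAP 5.2.1, repeated as a footnote to the Capability table, saying that higher scores mean worse function.

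The cost is one question number, one sentence and one footnote in the SAP, plus one word in the protocol or one line in SAP 1.1. No data collection or additional analysis is needed. SAP section 1 requires the final SAP to be approved before database lock, so the change belongs before that point.
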